1. PROGRAM SUMMARY

Please provide a brief summary of your grant project including the needs to be addressed, the services provided, and the population served.

Services delivered by the TYRO Champion Dads (TCD) Project are designed to address the skills fathers may need to promote healthy relationships and economic stability in their families. The target population for this project is low-income fathers who identify as Hispanic or Latino, are 18 years of age or older, have no open criminal cases (can be deferred), and have at least one child up to 24 years of age. The primary components of the TCD project are:

1. **Education-based curricula**—TYRO Dads and Core Communication—are delivered as primary services to improve the parenting, co-parenting, partner relationship, and financial skills of all TCD participants. Participants assigned to the treatment group also receive the Ray of Hope curriculum to mitigate risk factors for domestic violence.
2. **Support services** are offered through case management and Anthem's Mini Clinic workshops to increase the likelihood that TCD participants benefit from primary services. Participants can walk in during normal business hours without an appointment to address an array of additional self-perceived needs not met by primary services with a menu of classes delivered on site or referrals.
3. **Cycles of Continuous Quality Improvement (CQI)** are carried out by the CQI Team to ensure that program and evaluation target goals are being met.

2. EVALUATION GOALS

Please briefly describe key goals of your evaluation and what you hope to learn below.

This impact evaluation aims to determine if the addition of the Ray of Hope curriculum is effective at improving outcomes among those program participants who are randomly assigned to the treatment group. Both treatment and control groups will receive standard TCD services under a shared condition, but only treatment group participants will be offered the additional Ray of Hope curriculum focused on mitigating risk factors related to domestic violence.

Standard TYRO Champion Dads (TCD) services deliver TYRO Dads and Core Communication curricula to help fathers build the skills necessary to engage in behaviors that promote healthy relationships and economic stability in their families. Standard TCD services were adapted from the TYRO Suite of curricula—TYRO Dads, Couples Communication I, and Couples Communication II — which were developed by a Christian, non-profit organization in Ohio called The RIDGE Project, for delivery in a classroom setting, as part of their mission to improve functioning of families affected by the incarceration of a father.

Standard TCD services use facilitators trained by the RIDGE Project to deliver TYRO Dads curriculum in its standard form and the Core Communication curriculum which is adapted from the Couples Communication I curriculum (participants do not receive any form of Couples Communication II). The TYRO Dads curriculum uses cognitive restructuring to present life

lessons to help participants understand, accept, and implement a healthy model of parenthood by resolving key issues—emotional, employment, financial, relationship, and others—that prevent them from meeting their familial obligations. The Core Communication curriculum helps participants develop the basic communication, cooperation, and conflict management skills necessary for successful relationships of all types, such as work, family, and others.

Standard services in the TYRO Champion Dads (TCD) Project directly address healthy relationships and economic stability for the families of participants, but not the dynamics of domestic violence that might be present in families. As a result, fathers in the target population may benefit from additional curriculum focused on attitudes and behaviors associated with domestic violence and risk-related factors. Because family trauma is traditionally considered a private matter in the Latino community, domestic violence or related risk factors may not be adequately detected or addressed by the social service system among this population in particular (Cabrera et. al, 2015).

Anthem Strong Families (ASF) is offering the Ray of Hope curriculum as a supplement to standard TCD services to better meet the needs of populations that may have unmet needs to address domestic violence in their families. The *Ray of Hope* curriculum is designed to help participants develop communication and conflict management skills like *Core Communication* and *Couples Communication I* but is also evidence-based and adds a sharp focus on the dynamics of domestic violence and related risk factors.

This impact evaluation will compare outcomes between study groups related to co-parenting behaviors, parenting behaviors, parenting attitudes, and partner relationship behaviors (study goals 4-7 below). This evaluation will also include an implementation study (study goals 1-3 below).

Goal 1: determine if enrollment targets for the TCD Project were achieved for the treatment and control groups.

Goal 2: determine if the intended amounts of standard TCD services (*TYRO Dads, Core Communication*) were offered to and received by the control group.

Goal 3: determine if the intended amounts of enhanced TCD services (*TYRO Dads, Core Communication, Ray of Hope* curricula) were offered to and received by the treatment group.

Goal 4: determine if treatment group participants who receive enhanced TCD services report **healthier parenting attitudes** compared to control group participants who receive only standard TCD services immediately following TCD program completion. .

Goal 5: determine if treatment group participants who receive enhanced TCD services report **healthier partner relationship behaviors** compared to control group participants who receive only standard TCD services 6 months after TCD enrollment.

Goal 6: determine if treatment group participants who receive enhanced TCD services report **healthier parenting behavior** compared to control group participants who receive only standard TCD services 6 months after TCD enrollment.

Goal 7: determine if treatment group participants who receive enhanced TCD services report **healthier co-parenting behavior** compared to control group participants who receive only standard TCD services 6 months after TCD enrollment.

3. EVALUATION ENROLLMENT

Please provide the expected start and end dates for program and evaluation enrollment using the tables below. For impact studies, please indicate expected start and end dates for each study group.

IMPLEMENTATION EVALUATION		
Please leave blank if not conducting an implementation study.		
	Program Enrollment	Study Enrollment
Start Date	04-01-2021	05-20-2022
End Date	03-01-25	03-01-25
Definition	
Fathers who are 18+ years of age, have no open criminal cases (can be deferred), with children up to 24 years old
	
Fathers who are 18+ years of age, have no open criminal cases (can be deferred), with children up to 24 years old AND agree to participate in the study after informed consent

IMPACT EVALUATION			
Please leave blank if not conducting an impact evaluation.			
	Program Enrollment	Study Enrollment	
		Treatment Group	Comparison Group
Start Date	04-01-2021	05-20-2022	05-20-2022
End Date	06-30-2025	11-30-2024	11-30-2024
Definition	
Fathers who are 18+ years of age, have no open criminal cases (can be deferred), with children up to 24 years old
	
Fathers who are 18+ years of age, have no open criminal cases (can be deferred), with children up to 24 years old AND agree to participate in the study after informed consent AND were not referred to the program due to involvement in a domestic violence case
	
Fathers who are 18+ years of age, have no open criminal cases (can be deferred), with children up to 24 years old AND agree to participate in the study after informed consent AND were not referred to the program due to involvement in a domestic violence case

4. EVALUATION TIMELINE

Please include a timeline for key activities of the evaluation below. Example of activities may include IRB submission, staff training, waves of data collection, analysis period, and report writing and submission.

Evaluation Activity	Start Date	End Date
Hire Evaluation Staff : Project Manager (Senior Consultant), CQI Data Manager (CQI-DM)	1/15/2021	2/15/2021
Evaluation Staff Training : Performance Data Measurement and Management (PDMM), CQI Process, Study Activities, Evaluation Plans	1/22/2021	3/12/2021
Kickoff Meeting : introduce evaluation team to project staff and orient them to study activities	2/3/2021	2/28/2021
IRB Certification : evaluation and project staff complete human subjects training	10/1/2020	2/28/2021
Evaluation Plan : evaluation and project staff develop and submit evaluation plan	1/15/2021	2/19/2021
Survey Tools : evaluation staff develop OLLE Pre/Follow-up Surveys (nFORM items at baseline included on OLLE Follow-up)	10/1/2021	2/28/2021
IRB Approval : evaluation staff develop and submit relevant documents to Solutions IRB	3/1/2021	3/15/2021
CQI Team : form team and conduct ongoing bi-weekly meetings to start CQI Process	3/15/2021	7/1/2025
CQI Training : train the CQI-DM and CQI Team about PDMM and the CQI Process	1/22/2021	3/19/2021
Study Activities Training : present to project staff an IRB approved study protocol for consent, enrollment, and data collection.	3/1/2021	3/28/2021
Implementation Evaluation : collect nFORM data to track delivery of intended service amounts	05/1/2021	05/01/25
Baseline Surveys : ACS, nFORM Entrance, OLLE Pre	5/1/2021	05/31/24 for local evaluation surveys; nFORM surveys will continue as required by

		federal funder until conclusion of program services
Exit Surveys : nFORM Exit, OLLE Post	8/1/2021	08/01/24
Follow-up Surveys : OLLE Follow-up (with items from nFORM Entrance)	5/1/2022	05/31/25
Preliminary Implementation Report Submitted	5/31/2022	6/31/2022
1 st Manuscript submitted for publication	7/1/2025	12/31/2025
Final Report Submitted	04/1/2024	06/01/2025 for first draft with final report to be submitted before the conclusion of the grant cycle

* you may add rows by hitting the tab button, or right click and select insert row below

EVALUATION PLAN

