10.3. METHODS OF DATA COLLECTION

If the evaluation will collect multiple waves of data, describe the timing of these waves below. When describing follow-up periods, specify whether the follow-up period will be post-baseline, post-random assignment, or post-program completion.

Wave of Data Collection (e.g., baseline, short-term follow-up, long-term follow-up)	Timing of Data Collection
Baseline	Collected immediately following informed consent and enrollment – during orientation or before first primary workshop session
Post-test	Collected after the completion of the primary services programming – during or following the last workshop or session
Follow-up (6 months after enrollment)	Collected approximately six months after program enrollment

For each measure, describe how data will be collected detailing which data collection measures will be collected by which persons, and at what point in the programming or at what follow-up point.

Measure	Timing of Data Collection (baseline, wave of data collection)	Method of Data Collection	Who Is Responsible for Data Collection?	Impact Evaluations Only: Will Methods or Collection Procedures Differ by Study Group?	Administrative Data Only: Will data access require data sharing agreement?
On-line Local Evaluation (OLLE) and nFORM Baseline Survey	Baseline	Participant self-enters survey using online data collection program or on paper surveys if necessary	CQI Data Manager will proctor data collection and assist participants as necessary	No	
OLLE and nFORM Post-Test Survey	Post-Test (approx. 12 weeks after enrollment during last workshop session)	Participant self-enters survey using online data collection program or on paper surveys if necessary	CQI Data Manager will proctor data collection and assist participants as necessary	No	
OLLE Six Month Follow-up Survey	Six months after enrollment / baseline	Participant self-enters survey using online data collection platform and link – or – Phone interview data collection	MER Research Staff/ participant tracking team	No	

* you may add rows by hitting the tab button, or right click and select insert row below

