Parenting relationship behaviors	Has at least one child age 24 or younger, saw child within past month	Continuous (range from 1 to 5 where 1 is never and 5 is every day or almost every day)	nFORM entrance, OLLE follow-up	Par_Beh	Average of 10 to 11 survey items (depending on child age) that relate to frequency of positive interactions with participant's youngest child
Parenting relationship attitudes	Has at least one child age 24 or younger, saw child within past month	Continuous (range from 1 to 5 where 1 is always and 5 is never)	nFORM entrance, nFORM exit	Par_Att	Average of 6 survey items that relate to frequency of feelings about participant's youngest child
Parenting relationship behaviors	Has at least one child age 24 or younger, saw child within past month	Continuous (range from 1 to 5 where 1 is never and 5 is every day or almost every day)	nFORM entrance, OLLE follow-up	Parent_Fight	Reported frequency of fighting with child
Partner relationship behaviors	All survey respondents	Continuous (range from 1 to 5 where 1 is never and 5 is always)	OLLE pre-survey, OLLE post-survey, OLLE follow-up	Partner_Fight	Reported frequency of fighting with partner
Partner relationship behaviors	All survey respondents	Continuous (range from 1 to 5 where 1 is never and 5 is always)	OLLE pre-survey, OLLE post-survey, OLLE follow-up	Partner_Disagree	Average of 7 survey items related to frequency of disagreement with partner on different topics

Analytic approach

The main goal of this impact study is to assess the impact of the addition of the Ray of Hope curriculum intervention on participant attitudinal outcomes immediately following program completion, and behavioral outcomes six months after program enrollment, as compared to the impact of standard TCD services alone.

Participation benefits are defined by the primary and secondary outcomes presented earlier in the theory of change logic model and with research questions and hypotheses. Impact estimates are based on participant responses to the OLLE Follow-up Survey across randomly assigned study groups to compare primary and secondary outcomes between them 6-months after TCD Project enrollment. More positive outcomes for the treatment group will be attributed to the intervention given that other TCD services are delivered in the same ways to both study groups under a shared condition.

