For the implementation analysis, program fidelity will be descriptively reported by the percentage of enrolled participants who receive: 1) any primary workshops, 2) employment supports, 3) substantive service contacts, 4) referrals. The program aims to provide all participants each of these four program components, so the percentage of participants who receive each of these will be compared to the 100% benchmark. Number of substantive service contacts per participant will also be compared to the benchmark of 8 SSCs set by OFA for FIRE grantees.

Dosage will be measured by percent of target primary workshops participants attend on average (using 90% as a benchmark), and categories of attendance (initial, halfway, 90%, 100%) will be reported and compared to targets established by the program.

Handling missing data

Outcomes

When creating the composite measures for our behavior and attitude outcomes, we will create a composite score by taking the average of multiple individual items. For these measures, our current plan is to use 20% as a threshold for allowable missing items, based on guidance from evaluation technical assistance resources. This plan is contingent on the final distribution of missing data in our data set. If participants have more than 20% of items missing for a given construct, the respondent will be assigned a missing value for that construct and will be excluded from the analytic sample for that outcome. We will not be imputing truly missing values for outcomes. To create a construct score, the average will divide by the number of non-missing values in the construct.

For outcomes that use single survey items, participants who do not respond to that item on either the pre- or follow-up survey will be excluded from the analytic sample for that outcome.

Data for the implementation outcomes could be missing as a result of programmatic data entry issues. For the sake of this evaluation, we assume that any primary or support services received by a participant are being accurately logged into nFORM, so a lack of documented attendance, service contacts, referrals, etc. is indicative of lack of services (i.e., a participant not receiving the program components as intended).

Assessing non-response bias

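### If local (OLLE) baseline surveys stopped on 05/31/24 while randomisation ran to 11-30-2024, later fathers are excluded from Partner_Fight, their place in Partner_Disagree is unclear, and the stated 620 for R2 is not met

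*Protocol*

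**What the plan says.** Protocol section 3 (impact evaluation table) opens study enrolment on 05-20-2022 and closes it on 11-30-2024 for both groups.

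Protocol section 4 gives the end of the baseline surveys as "05/31/24 for local evaluation surveys; nFORM surveys will continue as required by" the federal funder until services end. The exit row ("nFORM Exit, OLLE Post") ends 08/01/24, and the follow-up row ends 05/31/25.

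Protocol section 10.3 describes the baseline wave as "Collected immediately following informed consent and enrollment – during orientation or before first primary workshop session" and places the post-test at "approx. 12 weeks after enrollment during last workshop session".

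The measure tables in Protocol section 10.1 and the SAP give the same sources for Partner_Fight and Partner_Disagree: "OLLE pre-survey, OLLE post-survey, OLLE follow-up". No nFORM source is listed for either.

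Under missing data, the SAP says of single-item outcomes that "participants who do not respond to that item on either the pre- or follow-up survey will be excluded from the analytic sample for that outcome". For composites the rule is different: "If participants have more than 20% of items missing for a given construct, the respondent will be assigned a missing value for that construct". That rule names no survey wave.

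Protocol section 9.3 states an analytic sample of 620 and a minimum detectable effect of 0.2 for every outcome, including the partner outcome. In section 9.2 that 620 includes Year 5 enrolees (35 analysed per arm).

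**The concern.** The two date entries cannot both govern. The baseline is taken at enrolment, so a father randomised after 31 May 2024 has no OLLE pre-survey if the timeline was followed. The timeline separates the local surveys from nFORM, so the nFORM continuation does not fill the gap for the partner measures.

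Partner_Fight is a single item, and the SAP drops any father who lacks the pre item. Partner_Disagree averages seven items, and the SAP does not say whether its baseline must be present. The plan would then randomise fathers whom it cannot use for part of a confirmatory outcome, while the power table still counts them.

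The cut-off is a calendar date that applies to both arms, so the main risk is lost power rather than bias.

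**Working it through.** **Inputs.** From Protocol section 9.3: one-tailed alpha 0.05, power 80%, effect 0.2 SD, total 620. Allocation is 1:1 (section 7). From section 9.2, analysed per arm: Year 2 49, Year 3 113, Year 4 113, Year 5 35, total 310. Dates are from sections 3 and 4.

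**Reproducing the plan's figure.** With z = 1.645 (one-tailed 0.05) and 0.842 (80% power):

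- n per arm = 2 × (1.645 + 0.842)² / 0.2², which rounds up to 310, so 620 in total. This matches.
- MDES = 2 × (1.645 + 0.842) / √N. At N = 620 this is 0.1997.
- Power at 0.2 = Φ(0.2 × √N / 2 − 1.645). At N = 620 this is 80.1%.

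**Share of fathers enrolled after the OLLE baseline cut-off.** The documents give no monthly accrual and do not date the grant years, so each of these is an assumption:

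- *Only Year 5 falls after the cut-off.* Loss = 2 × 35 = 70, which is 70/620 = 11.3%. Remaining: 550.
- *Even accrual over the window.* 05-20-2022 to 11-30-2024 is 925 days, and 05/31/24 to 11-30-2024 is 183 days. 183/925 = 19.8%, and 0.198 × 620 ≈ 123. Remaining: about 497.
- *Grant years start on 1 October.* All of Year 5 and June to September of Year 4 (4/12 = one third) are lost. Per arm: 35 + 113/3 = 72.7; in total 145.3, or 23.4%. Remaining: about 475.

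| Accrual assumption | Remaining N | Power at 0.2 | MDES |
|---|---|---|---|
| Plan as stated | 620 | 80.1% | 0.200 |
| Year 5 only | 550 | 75.8% | 0.212 |
| Even accrual | 497 | 72.1% | 0.223 |
| October grant years | 475 | 70.3% | 0.228 |

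These use the power table's own settings, with no multiplicity adjustment.

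**Which R2 measure is affected.** For Partner_Fight the pre-item requirement is explicit, so the table applies directly. For Partner_Disagree the SAP points both ways. Its sample definition asks for an entrance survey, which could be the nFORM one, and baseline values enter the model only where a group difference is found. Yet the non-response section defines a complete case as having both pre and follow-up surveys, and the hypotheses are judged on improvement. The table applies to Partner_Disagree only if an OLLE baseline turns out to be required.

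**Exit date.** R2 is measured at six months on the OLLE follow-up, which stays open to 05/31/25, so 08/01/24 does not touch it. R1 takes its outcome from nFORM Exit. Twelve weeks before 08/01/24 is 9 May 2024, and 205 of the 925 days (22%) lie after that. Those fathers are exposed only if nFORM Exit also stopped.

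**The case against.** The strongest reply is that the survey rows are old text and OLLE baseline collection never stopped. Section 4 shows other signs of loose dating: a survey-tools row that ends before it starts, and an end date of 6/31/2022. The baseline, exit and follow-up rows also all start before study enrolment opened. This stands as a possibility, so the loss must be stated conditionally. It does not remove the conflict, because the table still contradicts section 3.

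A reader might infer that the timeline was partly revised, since 05/31/25 falls six months after 11-30-2024. The documents do not support that. The baseline and follow-up rows differ by exactly 12 months at the start (5/1/2021 and 5/1/2022) and at the end (05/31/24 and 05/31/25), so they fit a single older schedule equally well.

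A reader might also infer that the last fifth of fathers cannot enter the partner analysis at all. Two parts of that fail. The exclusion is explicit for Partner_Fight only, and a fifth assumes even accrual, whereas the yearly table is uneven (70, 162, 162 and 50 randomised per arm).

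Finally, a reader might extend the loss to R1. The nFORM continuation note sits in the baseline row, but its wording is general, and Protocol section 12.1 lists Exit among the nFORM surveys. R1 is therefore a query and not a finding.

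**Conclusion.** The date conflict is real and bears on a confirmatory outcome. If 05/31/24 was applied, Partner_Fight loses every father randomised from June to November 2024, and the SAP leaves their status in Partner_Disagree open. On the accrual assumptions shown, the sample with an OLLE baseline is about 475 to 550 against the stated 620, power 70–76% against 80%, and the MDES 0.212–0.228 against 0.20. This is a moderate loss of precision.

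The documents do not establish that collection stopped, so they do not show that 620 was missed in fact. They show that the plan as written does not deliver it for Partner_Fight, and may not for Partner_Disagree.

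**What to change.** 1. Reconcile Protocol sections 3 and 4, and report the actual end dates of OLLE baseline and exit survey collection. The SAP is dated 12/9/2024, after all the disputed dates, so the sponsor can state what happened. Writing 11-30-2024 into the baseline row without checking would record a date that the documents do not establish.
2. State for each partner measure whether an OLLE baseline is required.
3. If OLLE baseline collection ended before randomisation did, amend the SAP missing-data rule so that fathers with a follow-up partner answer stay in both R2 analyses. Where the baseline value is a covariate, a missing-baseline indicator is one way to do this.
4. Restate N and MDES for any R2 analysis that still requires an OLLE baseline. Do the same for R1 only if nFORM Exit also stopped.

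The cost is the corrected dates, one SAP sentence, and possibly a slightly less favourable figure for R2.
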